4.11 Data Management

Study data will be managed using customized Research Electronic Data Capture (REDCap) tools hosted at the University of British Columbia, with secure access by all investigators in Uganda and Canada. REDCap is a secure, web-based application designed to support data capture for research studies. Data will be entered into the REDCap database by a trained research nurse or research assistant after each activity is completed and audio recordings are transcribed. Members of the study team will ensure that the rights of subjects and confidentiality of data are protected and respected. Research assistants will be trained on how to keep data secure and confidential during direct-observation activities. No information that discloses the identity of participants will be released or published without their specific consent to the disclosure. However, research records identifying participants may be inspected in the presence of the Investigator for the purpose of monitoring the research. No records which identify the participants by name or initials will be allowed to leave the Investigators' offices. Each participant will be assigned a personal identifier to collect discharge process and follow-up data. All paper-based and digital audio recording data will be stored in a locked cabinet in a locked office at Walimu. Access to identifiers will be limited to those requiring this data for follow-up (i.e., only study personnel involved in telephone interviews). No analysts, co-investigators or principal investigators not directly involved in the follow-up will have access to this data. Access to identifiers will require 2-way authentication: in addition to the normal password process, a secure code (sent via SMS to the user) will be required for access to this data. Identifiable data will be securely stored and destroyed after 10 years.

After the study period, a de-identified copy of the data will be prepared for deposition in a repository with open access with proper governance mechanisms. We will make every effort to prevent re-identification of subjects by coding data that has the potential of being identifiable. For example, we will convert all dates into meaningful decimal numbers (date of birth into days since birth and date of recruitment will be reduced to month of recruitment) and all locations will be coded into data that is useful but not specific (such as address converted to distance and

direction from facility). We will ensure that data elements with small numbers of subjects (less than 10) will be coded or lumped to avoid identification. The de-identified study data will be made available using a data hosting service (e.g., the Pediatric Sepsis Data CoLaboratory's Scholar's Portal Dataverse, Vivli, etc.)

(https://dataverse.scholarsportal.info/dataverse/Pedi_SepsisCoLab). Scholar's Portal Dataverse is a virtual archive for Canadian research data with a rigorous data governance structure. To gain access to the Sepsis CoLab's Dataverse, members must first sign a Memorandum of Understanding, whereas access to de-identified patient data requires signing a data sharing agreement. Data will also be shared through peer reviewed publications.

5.0 CHAPTER FIVE: Ethical considerations

5.1 Ethical Review and Approval Process

We will obtain ethics approval from the Makerere University School of Public Health (MakSPH) Institutional Review Board, the Uganda National Council of Science and Technology (UNCST) in Uganda and the University of British Columbia in Canada. Any future revisions to study procedures will be submitted as formal amendments and approved by the MakSPH IRB and the University of British Columbia prior to implementation. Administrative clearance will also be obtained from the respective hospitals, and informed consent will be obtained from all participants before data collection begins.

5.2 Informed Consent

Written informed consent will be obtained from all study participants, as well as the parents or guardians of eligible minor participants. A signed and dated copy of the consent form will be kept in the documentation file at all times. All participants will be aware of the study rationale, as well as any potential risks. The consent forms make it clear that standard care will not be compromised if they do not consent to participate in this study. Consent will be obtained from minors following local protocols, which is to consider underage girls as emancipated minors with full independence to consent to participating in research. Obtaining written informed consent from minors will also require a parent/guardian signature or thumbprint. Participants and parents will voluntarily sign and date the consent form if they wish to participate in the study and will be provided with a copy of the consent form. There will be five separate consent forms: one each for minors and non-minors participating in the observational cohort study, one for healthcare workers participating in process mapping, and one each for minors and non-minors participating in focus group discussions. Consent forms will be available in English, Runyankole and Lusoga (the English versions of these forms are included with this protocol; they will be translated into other languages prior to the study start date). Patients/caregivers enrolled in journey mapping will be provided with a bar of soap and a kilo of sugar as a token of appreciation for their time participating in the study. Caregivers participating in FGDs will be provided with 30,000 UGX each to compensate for their time and transportation costs.

5.3 Risks/Benefits to Participants

This is a minimal-risk study, as defined by all relevant ethics review boards in Canada and Uganda. The overall risks to participants are similar to those associated with standard clinical practice for facility deliveries and postnatal care. All dyads will receive routine care throughout their admission, in accordance with local hospital policies and national health guidelines. No study procedures will interfere with standard care, and consent will not be sought until after the patient has received an initial assessment by health workers. Relevant collected data (e.g., anthropometric data, vital signs) will be available to health workers for use during clinical care. Mothers or family members of dyads enrolled in the study may have painful memories triggered during follow-up, especially if the mother or newborn has died. To minimize this risk, all study staff will undergo empathy training and training on protocols for scenarios of extreme distress. If a mother is concerned about their health or the health of their child during follow-up, they will be referred to the nearest health facility or community health worker for assessment.

Risk of COVID-19 infection remains an ongoing concern. Study staff will follow all public health orders and infection control procedures at our study sites to reduce the spread of infection between staff and between staff and patients. Further, we will develop and implement a study-specific COVID-19 risk mitigation plan outlining study-specific infection control measures and protocols for contact tracing and follow-up for any confirmed or suspected COVID-19 cases among study participants and staff.

References

3. United States Agency for International Development. (2016) 'Ugandan Demographic Health Survey report" <https://dhsprogram.com/what-we-do/survey/survey-display-504.cfm> Accessed December 5, 2017

Appendix A: Variables Collected

Table 6. Variables Collected

Time Period	Data Collection Tool	Variables
Admission	Admission Variables	Maternal Age
		Refereed
		Who decided it was time to come to the hospital
		How long did it take to get to the hospital (hours)
		Mode of transport to the hospital (walk, motorcycle, private vehicle, ambulance, etc.)
		Date and Time of admission
		Does the woman know her approximate due date?
		How was the due date defined (LMP, not sure, ultrasound, woman herself, missing)
		Due date (if known)
		Admission vital signs (temperature, BP, HR)
Admission	Health & Pregnancy History	Were you delayed >1 hour by any of the following: 
 a. Terrain (boat, swamp, flood, etc) b. Cost of transport c. General transport delay (waiting for bus, schedules, etc.)
		Number of pregnancies in lifetime
		Number of pregnancies with baby born greater than 500g and 20 weeks gestation
		Chronic health conditions before pregnancy
		HIV related details during pregnancy (new diagnosis, ARV, etc.)
		Malaria with antimalarials during pregnancy
		Conditions diagnosed during pregnancy - select all that apply (diabetes, pre-eclampsia, eclampsia, hypertension, antepartum hemorrhage/vaginal bleeding, PPROM, preterm labor, malaria, HIV, UTI, TB, Anemia, Other infection, None)
		Admission during pregnancy, duration (no, <28 days, >28 days), reason
		Taking medication for (high blood pressure, antimalarial, ARVs, antibiotics)
		Sought care from traditional birth attendant
		Took herbs while pregnant
		Saw a midwife, nurse, doctor for ANC care
		Number of times ANC care was sought with midwife, nurse, doctor
		Prenatal vitamins during pregnancy

		Prior admissions (number of admissions, date, length of stay, self-reported diagnosis during admission)
		UTI history, if yes: 
 a. If admitted – where/when? b. IV antibiotics – Yes/No c. Other?
		Pre-delivery hematocrit
		Substance use – select all that apply (smoking, alcohol, other drugs)
		Did you take any of the following while pregnant: Abx, antimalarials, antihypertensives, ARVs, prenatal vitamins, herbs
		During your pregnancy, did you or any household member have to eat less food than you felt you was needed?
		Abortion history – Yes/No
		Previous caesarian section – Yes/No
		Previous infertility – Yes/No
		Known placental disorders
Delivery	Maternal Variables	Date/Time of delivery
		Mode of delivery
		Episiotomy – Y/N
		Vaginal tearing and recorded degree of tearing
		Induced labour and method of induction
		PPH noted (estimated blood loss, blood transfusion needed, how many units of blood)
		Obstructed labour
		Meconium in amniotic fluid
		Number of babies delivered
		Number of vaginal exams (self-reported)
		Date/Time labour started
		Fetal position
		Administration of oral fluids, IV fluids, and antibiotics
		Placenta disruptions (placental previa, placental abruption)
		Number of vaginal exams
		Early or delayed cord clamping
Delivery	C-Section Variables	Before anesthesia (Y/N): special procedures needed (central line, art line), Hb, platelet, glucose, magnesium, antibiotic prophylaxis (cefazolin, azithromycin, other)
		Before skin incision (Y/N): Antibiotics were given and when, plan for post-op analgesia, gestational age, reason for c section, pregnancy issues,

		medications (anesthetics, opioids, magnesium, betamethasone, other), early or delayed cord clamping
		Debriefing: VTE prophylaxis checklist, anticoagulation and timing, placenta pathology, special management needed, blood loss, urine output, fluid intake
Delivery	Neonatal Variables	Baby born alive
		Sex of the baby
		Apgar score 1 minute
		Apgar score 5 minutes
		Weight of the baby (kg)
		Resuscitation with oxygen therapy at birth
Discharge	Maternal Variables	Have you been able to start breastfeeding
		Systolic BP
		Diastolic BP
		SpO2
		HR
		Respiratory Rate
		Temperature
		Hematocrit
		Discharge status (routine, AMA, referral, death, other)
		Symptoms at maternal interview check all that apply (headache, visual changes, chest pain, shortness of breath, nausea and vomiting, abdominal pain, foul smelling vaginal discharge, stiff neck, cough, difficulty emptying bladder)
		During this admission was she given antibiotics (Y/N) also add route (IV/PO)
		Date/Time of discharge
		Scheduled follow up date
		Lab tests conducted Y/N & results
Discharge	Neonatal Variables	Intent for minimal outside contact with community for first 6 weeks
		Baby being discharged with mom
		Disposition of baby – admitted to NICU, died, referred, other.
		Baby pooped
		Baby peed
		Length
		Head circumference
		Weight
		Temperature

		SpO2 Right hand/any foot
		Date, time of discharge and follow up captured under maternal
		Discharged on antibiotics?
Discharge	Maternal Socioeconomic Variables	Residence (District, Other District, Sub-county, Other Sub-County, Parish, Other Parish, Village, County/Constituency, Chairman captured)
		Number of people in household
		Number of children in household including baby
		Marital status
		Do you live with the father of the baby
		Maternal level of education (no school, P4-7, S1-6, post-secondary)
		SES Index (score out of 8), includes the following questions
		
 a. Finished floor material b. flush toilet c. LPG/electricity for cooking fuel d. improved source of drinking water (with defn) e. more than one room in home f. electricity g. television h. refrigerator i. smart phone j. car, motorbike, bicycle, truck
		Have any other of your children died – Y/N
72-hour post-discharge	Maternal and Newborn Follow-up Telephone Interview	Travel time from hospital to home
		Mode of transport from hospital to home
		Did the time of discharge affect trip home?
		Barriers encountered on journey home
		Patient experience measures (Likert scales – e.g., felt healthcare worker spent enough time preparing them for discharge, were things explained in a way that was easy to understand, quality of discharge experience, etc.)
6 weeks post-discharge	Maternal Variables – Follow-up Interview	Is the mother alive
		Did she seek care at any time after being home post delivery
		How many routine postpartum visits were made after discharge following birth
		Number of days after birth first PNC visit was made
		Admitted for one or more nights for any reason after being home with her baby post-delivery
		During admission any of the following (vaginal bleeding, abnormal tiredness, convulsions, shortness of breath, vision changes, severe headaches, abdominal pain, abdominal tenderness, foul smelling

	vaginal discharge, fever/body hotness, diarrhea, vomiting everything, cough, loss of consciousness, other)
	Diagnosis (was she told she had pre-eclampsia, eclampsia, HIV, malaria, heavy bleeding, surgical site infection, puerperal sepsis, other infection, diarrhea, vomiting, PPD/psychosis, other)
	Admission date
	Number of nights she was in hospital due to these conditions
	Was hospital care sought prior to her death?
	Was the care sought for routine postpartum follow-up?
	How many routine postpartum visits were made after discharge following birth?
	How many days after birth was the first PNC visit made?
	Did mom get sick during first 6 weeks (Y/N)
	If yes, did she seek care (Y/N)
	If yes, was she re-admitted (Y/N – also how many times and when)
	During this illness, did she experience any of the following symptoms
	Are you based in the same home that you were in prior to delivery
	Support present during post-partum period (list: ex. mother, mother-in-law, etc.)
	Verbal autopsy for mothers who die
6-week post-discharge	Neonatal Variables – Follow-up interview
	Is the newborn alive at the time of the follow up interview
	Did the newborn die without ever having been discharged following birth
	Date of death
	Place of death
	Was hospital care sought prior to their death
	How many PNC check-ups were completed after leaving the hospital following birth
	How many days old was his baby when the first PNC check was done after leaving the hospital following birth
	Was the newborn admitted for one or more nights at a facility for any reason after being home post-delivery?
	Number of days from discharge till readmission
	Symptoms during illness (rash, cough, diarrhea, fever/hotness of body, vomiting everything, abnormally sleepy, changes in urine colour, making less urine than usual, blood in stool, seizure/convulsions, yellow soles, feeding status, no symptoms, don't know)
	Baby's feeding/drinking status currently

	For how many weeks after delivery was the child exclusively breastfed?
	Is child being exclusively or Non-exclusively breastfed
	For neonates who were readmitted were you told the child had (sepsis, respiratory distress, endocrine/metabolic disease, trauma/injury)
	Are they still in hospital due to this/these conditions
	How many nights were they in hospital due to this/these conditions?
	Did you seek care for the newborn at a facility at any time after being home post-delivery?
	Was this care for routine vaccinations or postnatal baby check-ups?
	How many postnatal baby check ups were completed after leaving hospital following birth?
	How many days old was this baby when the first postnatal check was done after leaving hospital following birth?
	For children who died: Verbal autopsy
	Timing of PNC visits: time from discharge to PNC visit and subsequent visits

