Currently, the World Health Organization (WHO) recommends three in-person postnatal visits for all mothers and newborn infants born at a health facility within the first six weeks of life⁶. The evidence used in formulating this recommendation is primarily based on timing of maternal and neonatal deaths and evidence surrounding the efficacy of the components of care recommended during the postnatal period. Despite this WHO recommendation, achieving any postpartum follow-up care has been challenging in many low-resourced settings. For example, in Uganda, only 57% of women received one visit with a skilled health care provider within 41 days of delivery³. There is an important opportunity to tailor recommendations for timing and frequency of follow-up to individual risk, to guide the use of scarce healthcare resources. Personalized risk scores can help frontline healthcare providers identify high-risk dyads before discharge from hospital, and guide recommendations for essential PNC. This approach facilitates safer hospital to home transitions and efficient allocation of scarce resources. Adherence to the recommended PNC visits is critical for those at higher risk.

The development of an evidence base upon which to build recommendations for the timing and intensity of postnatal care in resource-poor countries is urgently needed. This study aims to address this gap in care coverage using a precision medicine approach to postpartum follow-up. Our approach to risk stratification integrates data about the health of both the mother and newborn. This ensures that when one is sick, the other can be more closely monitored to prevent their potential decline in health. We are working to expand our innovative precision public health approach to improving post-discharge care for mother-newborn dyads. Our aim is to build a discharge risk prediction score that identifies high-risk dyads before hospital discharge. To achieve this, we will conduct an observational cohort study in 7,000 dyads discharged together after live births at JRRH and MRRH. With the data collected from this study, we will be able to develop prediction models with up to 30 candidate predictors for both maternal and newborn outcomes separately.

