4.4 Study Population

Phase I: Observational Cohort Study

We will recruit 7,000 mother and newborn dyads from the two participating hospitals. Based on previously observed outcome and loss to follow-up rates, we will be able to measure the prevalence of maternal and newborn hospital readmission or death within a margin of error of 1% and develop prediction models with up to 30 candidate predictors for both maternal and newborn outcomes separately with this sample size.

Inclusion:

- Women and adolescent girls aged 12 and above delivering a single or multiple babies at the study hospital during the active recruitment phase.

Exclusion:

- Inability, for whatever reason, to provide informed consent.
- Language barrier
- Mother is from a refugee camp
- Mother has no access to phone or other means for follow-up
- Mother lives outside of hospital catchment area

We will continue to follow-up with all patients enrolled in the study. This includes enrolled mothers whose baby dies after discharge as well as enrolled babies whose mothers die. In the event that the mother dies, we will follow-up with the caregiver of the baby.

Table 3. Phase I sample size

Participants:	Sample size (n=7,000)
Maternal Infant Dyads	3,500 per facility (n=7,000)

Phase II: Patient Journey Mapping

We will randomly select 100 mothers (50 per facility) from the phase I cohort of 7,000 dyads to participate in journey mapping due to intense time to capture.

Inclusion:

- Women and adolescent girls aged 12 and above delivering a single or multiple babies at the study hospital during the active recruitment phase.
- Enrolled in Phase 1.

Exclusion:

- Inability, for whatever reason, to provide informed consent.

Exclusion:

- Inability, for whatever reason, to provide informed consent.
- Language barrier
- Mother is from a refugee camp
- Mother has no access to phone or other means for follow-up
- Mother lives outside of hospital catchment area

Table 4. Phase II sample size

Participants:	Sample size (n=100)
Maternal Infant Dyads	50 per facility (n=100)

Phase III: Process Mapping

We will purposively select a sample of 6 healthcare providers and 2 hospital administrators from each of the 2 study sites for participation in a process mapping exercise based on their level of experience, availability, and consultations from site leads (Table 4).

Inclusion:

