4.6.3 Study Procedures

Phase I: Observational Cohort Study

I. Admission

- a. The study team will collect admission variables and health and pregnancy history through chart review and interviews with the participant. Data will not be collected during periods of maternal stress. In this case, incomplete interview questions will be deferred to the discharge interview.
 1. Admission variables: These questions include mode of transport, maternal demographic and socioeconomic variables (e.g., distance travelled to the hospital, age, location of residence). Data collected will also include vital signs (e.g., temperature, blood pressure, heart rate).
 2. Health and pregnancy history: This includes questions on number of previous pregnancies, comorbidities, prior admissions, and medication history.

II. Delivery

- a. Maternal variables: The study team will collect data related to the delivery including mode of delivery, method of induction, noted vaginal or perineal tearing, and any other major events or conditions occurring during delivery.
- b. Neonatal variables: Data will be collected related to the delivery including sex, Apgar score, weight, and resuscitation with oxygen therapy at birth.

III. Discharge

- a. Clinical Data Collection: A maternal and neonatal clinical examination will occur prior to discharge.
 1. Maternal Clinical Exam: Research nurses will record clinical signs and symptoms including SpO₂, heart rate, blood pressure, respiratory rate, and body temperature. We will also collect a small sample of blood (200 microlitres) to test hematocrit levels.
 2. Neonatal Clinical Exam: Research nurses will record clinical signs and symptoms data including weight, SpO₂, body temperature, and urination and defecation status. Data will also be collected on the infant's health status prior to discharge including NICU admission.
- b. Patient Interview: Following delivery, and prior to discharge, research nurses will conduct a structured interview and collect data including breastfeeding status, any symptoms experienced (e.g., headache, chest pain, difficulty emptying bladder, etc.).

IV. 6 Week Maternal and Newborn Follow-up (Outcomes)

- a. Telephone Interview: Research nurses and field officers will follow-up all dyads at 6 weeks postpartum to collect data on post-discharge care seeking and health outcomes, as well as newborn care practices. A verbal autopsy will be performed in all cases of newborn or maternal death. If

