Appendix D: Neonate Outcomes

Table 8. Neonatal Outcomes (n=134)

Readmission n=108	n (%)
Diagnosis	
Sepsis	68 (63.0%)
Respiratory distress	21 (19.4%)
Endocrine/Metabolic Disease	2 (1.9%)
Trauma/Injury	2 (1.9%)
Deaths n=26	
Period from delivery to death (days) median [interquartile range]	5.00 [3.00-14.8]
Period from discharge to death (days) median [interquartile range]	4.00 [1.25-13.8]
Location of death n (%)	
Home	9 (34.6%)
Hospital	13 (50.0%)

En route to hospital	4 (15.4%)
Was hospital care sought prior to death n (%)	
Yes	16 (61.5%)
No	10 (43.5%)
Symptoms (n=131)	
Fever/hotness of body < 7 days	72 (55.0%)
Cough < 14 days	7 (5.3%)
Fever/hotness of body > 7 days	5 (3.8%)
Abnormal sleeping	5 (3.8%)
Changes in urine color	4 (3.1%)
Seizure/Convulsions	4 (3.1%)
Diarrhea < 14 days	3 (2.3%)
Rash	12 (9.2%)
Vomiting	10 (7.6%)
Yellow Soles	10 (7.6%)
None of these symptoms	10 (7.6%)
Cough > 14 days	1 (0.8%)
Diarrhea > 14 days	1 (0.8%)
Less urine than usual	1 (0.8%)
Blood in stool	1 (0.8%)
Unknown	1 (0.8%)

Table 9. Neonatal Care Seeking

Care Seeking n = 131 (108 readmitted+23 dead)	
Did you seek care for the newborn at a facility after being home post delivery n (%)	
Yes	108 (82.4%)
No	0 (0%)
Missing	23 (17.6%)
How many post natal baby check ups were completed after leaving hospital following birth	
0	3 (2.3%)
1	1 (0.8%)
2	33 (25.2%)
≥3	50 (38.2%)
Missing	44 (33.6%)

How many days old was this baby when the first post natal check was done after leaving hospital following birth median [interquartile range]	8.00 [3.75-21.0]
Number of days from discharge to readmission median [interquartile range]	2.00 [0-8.00]

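### The newborn's discharge date is the mother's, so discharge-based timing is wrong or uncheckable for infants who do not leave hospital with her

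*Combined protocol and SAP*

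**What the plan says.** In Appendix A, Table 6, the maternal discharge block records one date and time of discharge. The neonatal discharge block has no date of its own and points to the mother's: "Date, time of discharge and follow up captured under maternal". That neonatal block also has a joint-discharge item, "Baby being discharged with mom", and a list for the other cases: "Disposition of baby – admitted to NICU, died, referred, other". No later item records when a retained or referred infant leaves hospital.

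At follow-up, the mother's list includes a readmission date. The newborn's list has no readmission date; it has "Number of days from discharge till readmission". It also has a date of death, the infant's age at the first postnatal check, and the time from discharge to postnatal visits.

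On who is in the cohort, chapter 1 describes "7,000 dyads discharged together after live births at JRRH and MRRH". The inclusion criterion in section 4.4 is "Women and adolescent girls aged 12 and above delivering a single or multiple babies at the study hospital during the active recruitment phase". Neither it nor the exclusion list requires mother and baby to leave together. Section 4.5 keeps mothers of severely ill infants and lets them defer the interview.

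Section 4.6.3 schedules a maternal and a neonatal examination before discharge, without saying whose discharge. It adds: "Data will also be collected on the infant's health status prior to discharge including NICU admission". Section 4.8 sets the primary outcome window at six weeks from birth, while two of the secondary outcomes use a six-week window after discharge.

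**The concern.** The form anticipates infants who do not leave with the mother, then gives them her discharge date. For an infant who stays in NICU or is referred, and for a twin who leaves on a different day from its sibling, that date falls on a day when the infant may still be an inpatient.

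Two things are at stake. The first is timing. The newborn interval to readmission, the interval to postnatal visits, and the age at which a newborn readmission occurred all depend on a discharge date that the study does not hold for these infants. The second is predictor measurement. The newborn score is meant to be used before the infant goes home, so its discharge predictors (weight, temperature, oxygen saturation) should describe the infant at that point. If they are taken when the mother leaves, they describe a retained infant in a different state.

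**Working it through.** No sample-size or power figure depends on this point, so the check is mainly textual, followed by simple arithmetic for scale.

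**1. What is dated, for whom (Appendix A, Table 6)**
- Mother: discharge date and time, and a readmission date. Her interval can be calculated and checked.
- Newborn: no discharge date and no readmission date, only a reported number of days between the two.
- Newborn deaths carry a date, so they can be placed from birth. The gap concerns readmissions and discharge-based visit intervals.

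**2. What the missing date does**

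Let M be the infant's age in days at the mother's discharge, C its age at its own discharge, and L = C − M, the lag. Let k be the reported number of days from discharge to readmission. The plan does not say which discharge the caregiver should count from.
- If the caregiver counts from the infant's own discharge, the interval k is right and the true age at readmission is C + k. The study can only compute M + k, which is too low by L. A readmission is wrongly placed inside six weeks (42 days) of birth when M + k ≤ 42 < C + k.
- If the caregiver counts from the mother's discharge, M + k is the right age, but k overstates the infant's own post-discharge interval by L.

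Either way one of the two quantities is off by L. Because C is not recorded, L is unknown and the error can be neither corrected nor detected. When infant and mother leave together, L = 0 and there is no problem.

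The six-week placement matters most if the interview is held six weeks after discharge, as section 4.1 and Appendix A state. Section 4.6.3 places it at six weeks postpartum, where an interview on schedule would itself limit reported readmissions to about that window.

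**3. When the predictors are taken**

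Section 4.6.3 does not say whose discharge fixes the neonatal examination. Three features of the form point to the mother's: it asks whether the baby is leaving with her, it offers NICU admission as a disposition, and it takes its date from her. No second neonatal examination is listed. This is a strong inference, not a stated rule.

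**4. Scale**

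The documents do not give the share of infants who do not leave with the mother. As an assumption:
- 5%: 0.05 × 7,000 = 350 dyads.
- 15%: 0.15 × 7,000 = 1,050 dyads.

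These are dyads with a non-matching date, not misclassified outcomes. For a rough idea of affected readmissions, the prior cohort had 108 newborn readmissions (Appendix D) among 2,926 dyads (section 2.1): 108 / 2,926 = 3.7% (section 2.1 prints 3.6%). If that rate also held in split-discharge infants, 350 × 0.0369 ≈ 13 and 1,050 × 0.0369 ≈ 39 readmissions would have uncertain timing, before losses. The true rate in this group is unknown and may differ. For comparison, the whole cohort would give 108 / 2,926 × 7,000 ≈ 258 newborn readmissions before losses.

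**The case against.** The strongest reply is that chapter 1 describes a cohort of dyads who leave together. If that governs, a shared date is coherent, apart from multiples leaving on different days. But sections 4.4 and 4.5 and the form itself do not apply that restriction, so the documents conflict. Either the criteria or the form needs a change.

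Several further replies stand and limit the point:
- A reader might infer that the primary outcome clock starts while the infant is still an inpatient. It does not: it starts at birth, and the modelling examples in section 4.10 are classifiers, not time-to-event models from discharge.
- A reader might infer that the index NICU stay would be counted as a readmission. The newborn item counts only admissions after the baby has been home, and a separate item identifies newborns who died before any discharge.
- A reader might see misdating in the prior cohort, where the lower quartile of newborn days from discharge to readmission is 0 (Appendix D, Table 9). The documents do not support this. Using an earlier maternal date for a retained infant would lengthen the interval, not shorten it to zero, and the prior cohort's forms and date rules are not shown.
- A reader might infer that the newborn model would look better than it will be in use. Nothing in the documents shows the direction of any bias. NICU status and disposition are recorded, so these infants can be identified and analysed separately.
- The interval is an interview item, and a caregiver may well count from the infant's own discharge. That would make the interval right, but not the age computed from it, and it could not be verified.

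**Conclusion.** The concern holds in a limited form. Taking the newborn's discharge date from the mother, with no newborn readmission date, leaves discharge-based newborn intervals and the six-week placement of newborn readmissions wrong or uncheckable for infants who leave on a different day from the mother. For the same infants, the discharge predictors probably describe their state when the mother left. The primary window and the definition of readmission are not themselves affected, and dyads who leave together are untouched.

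The size depends on the unreported share of split discharges: 350 to 1,050 of 7,000 dyads at an assumed 5% to 15%. The conclusion also assumes that section 4.4 governs eligibility over chapter 1. If chapter 1 governs, what remains is to state joint discharge as a criterion and to handle multiples. The change is worth making because it is small, and dates not collected prospectively may be hard to recover.

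**What to change.** - Reconcile chapter 1 with section 4.4: state whether dyads who do not leave together are eligible.
- In Appendix A, Table 6, replace the shared-date row with each infant's own discharge date, time and status, entered per infant for multiples.
- Add a newborn readmission date to the follow-up interview, matching the mother's.
- Define newborn discharge-based intervals (to readmission and to postnatal visits) as counted from the infant's own discharge.
- If split dyads are eligible, either abstract the neonatal discharge variables from the chart at the infant's own discharge and use those in the newborn model, or report newborn model performance with and without infants who did not leave with the mother.

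The cost is a few extra form fields and, if the first option is chosen, chart abstraction for the infants concerned. Some values will be missing for infants referred elsewhere. A repeat bedside examination is not needed.
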